4.1 Inclusion criteria

Healthy male volunteers aged 18 and older with a body mass index $< 30 \text{ kg/m}^2$.

4.2 Exclusion criteria

Known or suspected neuromuscular disorders impairing neuromuscular function; allergies to muscle relaxants, anesthetics or narcotics; a (family) history of malignant hyperthermia or any other muscle disease; any medical, neurological or psychiatric illness (including a history of anxiety).

4.3 Drop out and replacements

Subjects that drop out will be replaced by a new subject. A subject may terminate the study at any moment, and will then receive sugammadex 2 mg/kg to ensure full reversal of the neuromuscular blockade. Subjects will then be paid (5 euros/h participation).

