4.5 Pre-study requirements

All subjects will be asked to refrain from food 6 hours prior to the study and from drinks 2 hours prior to the study.

5. Study design

This is a randomized, double blind, 3-arm, placebo controlled parallel study on the influence of reversal of a partial NMB on carotid body function following rocuronium administration. Healthy volunteers will be randomized to receive either placebo (Group1, n = 12), neostigmine (1 mg, n = 12) or sugammadex (2 mg/kg, n = 12) following a continuous rocuronium infusion for 120 min aimed at a TOF ratio of 0.8 for 1 h followed by 0.6 for another hour. Prior to the rocuronium infusion and during the infusion, ventilatory responses to isocapnic 2-min hypoxic pulses will be obtained as well as the (hyperoxic) ventilatory response to hypercapnia. After the 120 min infusion and the administration of reversal agents, the ventilatory response to hypoxic pulses will be obtained at 5 min interval for at least 60 min. In case the response has not returned to pretreatment control values, additional responses will be obtained. Hereafter, a final ventilatory response to carbon dioxide will be obtained (at hyperoxic conditions).

All procedures will be executed in compliance with the current revision of the Declaration of Helsinki and Good Clinical Practice guidelines. The trial starts after the medical ethical committee has approved the study protocol and will have a maximum duration of one year.

5.1 Rocuronium administration:

We will titrate rocuronium to effect followed by a target controlled infusion aimed at a TOF ratio of 0.8 and 0.6 (see Fig. 1). After 120 min the continuous infusion will be terminated. The plasma concentration and expected TOF ratio is simulated in Figure. 1.

[figure not shown]

Figure 1. Simulated plasma concentration (LEFT) and expected TOF ratio (RIGHT). A continuous infusion of rocuronium for 120 min (1st hours aimed at TOF ratio 0.8, 2nd hour TOF ratio 0.6). Additionally during the 1 hour period after reversal the timing of hypoxic challenges are given (vertical dotted lines).

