5.2 Reversal

At $t = 120$ min, all subjects will receive a reversal agent which is placebo (NaCl 0.9%) for Group 1, neostigmine 1 mg/atropine 0.5 mg for Group 2 and sugammadex 2 mg/kg for Group 3.

[figure not shown]

Figure 2. Examples of hypercapnic (left and middle) and hypoxic challenges in a healthy volunteer. From Dahan et al. Anesthesiology 1994.

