7.2 Sample size calculation

We decided not to use a crossover design as we do not want to expose one person to multiple awake rocuronium infusions. Hence we chose a parallel design. We powered the study on the speed of reversal of HVR from TOF ratio 0.6 to TOF ratio 1.0 between sugammadex and neostigmine. Assuming a return of carotid body function within 3-5 min for sugammadex and at least 10-20 min for neostigmine with a SD of the difference of 4-5 min we calculate the need for 12 subjects per group giving a power of > 90% ($\alpha = 0.05$). The power calculation was performed in SigmaPlot.

8. Monitoring

The subject will be closely monitored by measurement of the TOF ratio using the TOFF Cuff/TOF watch system, oxygen saturation, respiratory rate, tidal volume, and ECG. In case of an emergency sugammadex will be administered to overcome the muscle blockade.

9. Subject discomfort

Due to the mild level of relaxation some subjects may experience some muscle weakness and dysarthria. This is frequently seen in postoperative patients and is well accepted, especially when subjects are well coached during the period of mild muscle relaxation. In case the subject indicates that his discomfort is unacceptable the level of

relaxation will be reduced, as discussed in paragraph 6. In case the subjects demands termination of the study the reversal agent Sugammadex will be administered.

There are multiple studies on the use of muscle relaxants in volunteers, such as the Eriksson et al. (1993) study. Here we give some examples:

Schuller et al. **Response of bispectral index to neuromuscular block in awake volunteers.** Br J Anaesth 2015; 115: i95-i103: Rocuronium 0.7 mg/kg was administered causing full paralysis in unsedated volunteers.

Blokland et al. **Detection of attempted movement from the EEG during neuromuscular block: proof of principle study in awake volunteers.** Sci Rep 2015; 5:12815: Complete relaxation in awake volunteers. Study performed at RadboudMC.

Cedbøg et al. **Pharyngeal function and breathing pattern during partial neuromuscular block in the elderly: effects on airway protection.** Anesthesiology 204; 120: 312-25: TOF ratios of 0.7 in elderly (>70 yrs) unsedated volunteers.

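### Replacing subjects who leave after the reversal agent, with no rule for analysing them, could understate recovery half-lives for placebo and neostigmine

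*Combined protocol and SAP*

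**What the plan says.** Section 4.3 has one rule for drop-outs: "Subjects that drop out will be replaced by a new subject". It does not separate those who leave before the randomised reversal agent from those who leave after it. The same section adds: "A subject may terminate the study at any moment, and will then receive sugammadex 2 mg/kg to ensure full reversal of the neuromuscular blockade". Section 9 repeats this for discomfort: "In case the subjects demands termination of the study the reversal agent Sugammadex will be administered". Section 8 gives a second route: "In case of an emergency sugammadex will be administered to overcome the muscle blockade".

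Under Section 5.2, at t = 120 "min, all subjects will receive a reversal agent which is placebo (NaCl 0.9%) for Group 1", with neostigmine for Group 2 and sugammadex 2 mg/kg for Group 3. Before that point all arms have the same two-hour rocuronium infusion. Afterwards, hypoxic pulses are given every 5 min for at least 60 min, and for longer if the response has not returned to control (Section 5).

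Section 7.1 makes the time course of HVR return after reversal the main end-point and summarises it as a half-life from an exponential fit. The documents define no analysis set. They do not say whether a replaced subject's data are kept, how HVR values after withdrawal sugammadex are handled, whether the replacement takes the same arm, or whether drop-outs are reported by arm.

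**The concern.** Once the reversal agent has been given, the time a subject stays weak is close to what the trial measures. A slow recoverer is weak for longer and, under Section 5, is tested for longer, so he has more opportunity to stop. Section 3 expects this exposure to differ greatly by arm: within 2 min for sugammadex against 40-60 min for neostigmine.

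A subject who stops in the placebo or neostigmine arm receives the comparator's drug, so his recovery under the assigned agent can no longer be observed. If he is then left out and a completer takes his place, the arm has been selected on the outcome. If his values after sugammadex were kept instead, they would describe sugammadex rather than his arm. Both errors make the slower arms look faster.

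At stake are mainly the half-life estimates for placebo and neostigmine and the size of their difference from sugammadex.

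**Working it through.** **Inputs from the documents.** Section 7.2: HVR return in 3-5 min for sugammadex and at least 10-20 min for neostigmine, SD of the difference 4-5 min, 12 per group, power above 90%, alpha 0.05. Section 3, hypothesis C: 40-60 min for neostigmine. No drop-out rate is given, and no planning recovery time for placebo.

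**Step 1. The plan's own figure.** Two-sample t-test, two-sided alpha 0.05 (two-sided is assumed; the plan does not say).
- Smallest gap 10 - 5 = 5 min, with 5 min read as the SD of a difference between two independent subjects, so per-arm SD 5/√2 = 3.54: 12 per group, power 0.911.
- Gap 7 min, per-arm SD 5: 12 per group, power 0.906.
- Gap 5 min, per-arm SD 4-5: power at 12 per group only 0.833-0.649.

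So 12 per group is reproducible under the first two readings. The calculation has no drop-out term; replacement restores the number of subjects but not the subjects who were lost.

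**Step 2. Size of a selective loss.** Assumptions: neostigmine recovery time is normal with mean 15 min (midpoint of 10-20) and SD 5; only the slowest quarter leave, each with probability p; their data are not analysed; replacements come from the same distribution under the same rule. The 75th percentile is at z = 0.674, where the normal density is 0.318.

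Shift in mean = -SD × p × 0.318 / (1 - 0.25p)

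| p | Share of arm leaving (0.25p) | Shift |
|---|---|---|
| 25% | 6.25% | -5 × 0.25 × 0.318 / 0.9375 = -0.42 min |
| 50% | 12.5% | -5 × 0.50 × 0.318 / 0.875 = -0.91 min |
| 75% | 18.75% | -5 × 0.75 × 0.318 / 0.8125 = -1.47 min |

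**Step 3. Against the matching gap.** A neostigmine mean of 15 min and sugammadex at 3-5 min give a gap of 10-12 min. The range is 0.42/12 = 3.5% to 1.47/10 = 14.7%, or about 4-15%. In an exponential recovery, the time to a fixed fraction of control is proportional to the half-life, so the half-life would be understated in the same proportion as the time: 0.42/15 = 3% to 1.47/15 = 10%.

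**Step 4. Check by simulation.** 100,000 runs, per-arm SD 5, with the 1, 2 or 3 slowest neostigmine subjects dropped and 12 retained.

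| Slowest subjects replaced | Shift (min) | Power, true gap 7 min | Power, true gap 11 min |
|---|---|---|---|
| 0 | 0 | 0.907 | 0.999 |
| 1 | -0.70 | 0.865 | 0.999 |
| 2 | -1.21 | 0.824 | 0.998 |
| 3 | -1.65 | 0.778 | 0.997 |

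With no true difference, rejection rises from 0.05 to 0.072, 0.109 and 0.156, in the direction of neostigmine looking faster.

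**Step 5. Milder and slower cases.** If 10% drop out and only a quarter or half of them do so because of slow recovery, the shift is 0.29 or 0.51 min (SD 4.5). For the slower recovery of hypothesis C, with an assumed mean of 50 min and SD 10, the shifts double to about 0.8, 1.8 and 2.9 min on a gap of 45-47 min. If every drop-out occurs before t = 120 min, the shift from arm-dependent recovery is zero.

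**The case against.** The strongest reply is that selective loss may never happen. The documents give no drop-out rate and no reasons. All arms share the two hours of infusion, and Sections 6 and 9 provide for lightening the block in subjects who do not tolerate it, so many would be dealt with before the arms diverge. After t = 120 min the infusion is off and Section 6 expects all values to normalise within 90 min. The study is double blind. Completion pays 250 euros, against 5 euros per hour for stopping (Sections 4.3 and 4.4). Replacing a subject also need not mean deleting his data.

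Much of this stands. It lowers the likely number of late withdrawals, and it means that a reader who infers that the rule does remove slow recoverers goes beyond the text. Discarding the withdrawn subject's data is implied, not stated.

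It does not remove the risk. Lightening the block, as Section 6 describes it, is an adjustment towards a target TOF ratio under infusion. Once the infusion has ended, the response that Section 9 describes for a subject who wants to stop is sugammadex. Blinding does not prevent a subject from leaving because of weakness that he feels, and payment does not make leaving independent of recovery.

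A second fair objection is that Section 7.1 plans an exponential fit, not a time-to-return analysis, and that cutting off data at withdrawal is itself informative if slow recoverers leave. This stands and shapes the fix.

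**Conclusion.** The gap is real and is a cheap improvement to the plan. Section 4.3 allows replacement after the randomised agent has been given, and no analysis rule protects the main end-point from selection on recovery speed. Whether bias follows depends on two things that the documents leave open: whether anyone leaves after reversal because of persisting block, and whether his data are then left out.

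Under the assumed mean of 15 min and SD of 5, the understatement is about 0.4-1.5 min, or about 4-15% of the matching 10-12 min gap. At an 11 min true difference the powered comparison is hardly affected; the estimated half-lives still would be.

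Two stronger readings are not supported. A reader might infer that the rule could manufacture a sugammadex advantage. The bias runs the other way: losing slow placebo or neostigmine subjects narrows the difference. A reader might also set these shifts against the 5 min minimum gap in Section 7.2. That gap pairs neostigmine at 10 min with sugammadex at 5 min, not the 15 min mean used here. It is the least favourable corner of the planning ranges and would have to be presented as a separate scenario.

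**What to change.** - **Section 4.3:** limit replacement without analysis to subjects who leave before the reversal agent. After that point an extra subject may be added, but must not displace the withdrawn subject's data.
- **Section 7.1:** keep every subject who received a reversal agent in the randomised arm. Fit the planned exponential recovery model to all HVR values obtained before any withdrawal or emergency sugammadex, and exclude later values.
- **Section 7.1, sensitivity analysis:** because stopping may be related to slow recovery, repeat the comparison treating withdrawn subjects as slow recoverers.
- **Reporting:** list drop-outs by arm, time and reason.

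The cost is a few sentences in two sections, some incomplete HVR curves and less precise half-lives for those subjects. The right to stop and the treatment given on stopping are unchanged.

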4.4 Reimbursement

Subjects will be paid euro 250 for the completion of an experimental session.

4.5 Pre-study requirements

All subjects will be asked to refrain from food 6 hours prior to the study and from drinks 2 hours prior to the study.

5. Study design

This is a randomized, double blind, 3-arm, placebo controlled parallel study on the influence of reversal of a partial NMB on carotid body function following rocuronium administration. Healthy volunteers will be randomized to receive either placebo (Group1, n = 12), neostigmine (1 mg, n = 12) or sugammadex (2 mg/kg, n = 12) following a continuous rocuronium infusion for 120 min aimed at a TOF ratio of 0.8 for 1 h followed by 0.6 for another hour. Prior to the rocuronium infusion and during the infusion, ventilatory responses to isocapnic 2-min hypoxic pulses will be obtained as well as the (hyperoxic) ventilatory response to hypercapnia. After the 120 min infusion and the administration of reversal agents, the ventilatory response to hypoxic pulses will be obtained at 5 min interval for at least 60 min. In case the response has not returned to pretreatment control values, additional responses will be obtained. Hereafter, a final ventilatory response to carbon dioxide will be obtained (at hyperoxic conditions).

All procedures will be executed in compliance with the current revision of the Declaration of Helsinki and Good Clinical Practice guidelines. The trial starts after the medical ethical committee has approved the study protocol and will have a maximum duration of one year.

5.1 Rocuronium administration:

We will titrate rocuronium to effect followed by a target controlled infusion aimed at a TOF ratio of 0.8 and 0.6 (see Fig. 1). After 120 min the continuous infusion will be terminated. The plasma concentration and expected TOF ratio is simulated in Figure. 1.

[figure not shown]

Figure 1. Simulated plasma concentration (LEFT) and expected TOF ratio (RIGHT). A continuous infusion of rocuronium for 120 min (1st hours aimed at TOF ratio 0.8, 2nd hour TOF ratio 0.6). Additionally during the 1 hour period after reversal the timing of hypoxic challenges are given (vertical dotted lines).

5.2 Reversal

At $t = 120$ min, all subjects will receive a reversal agent which is placebo (NaCl 0.9%) for Group 1, neostigmine 1 mg/atropine 0.5 mg for Group 2 and sugammadex 2 mg/kg for Group 3.

[figure not shown]

Figure 2. Examples of hypercapnic (left and middle) and hypoxic challenges in a healthy volunteer. From Dahan et al. Anesthesiology 1994.

After approval of the protocol by the Human Ethics Committee a total of 30 volunteers will be recruited and tested in the Clinical Research Unit of the Department of Anesthesiology at Leiden University Medical Center. Each volunteer will undergo a physical examination first and only healthy volunteers without a (family) history of neuromuscular disease will be included in the study.

The subjects are not allowed to eat or drink for at least 8 hours before the experiment.

After arrival in the laboratory all subjects will be connected to monitors including ECG, pulse oximeter and two EMG electrodes to measure diaphragmatic EMG activity; next an iv line is placed. The subjects are comfortably seated in a semirecumbant position. Next, the control ventilatory responses are obtained. A facemask will be used to administer specific gas mixtures.

Following the control ventilator responses and after a short break the rocuronium will be titrated to a TOF ratio of 0.8 for 1 hour followed by 0.6 for the next hour. In case the TOF ratio of 0.6 has a large effect on the subject in terms of oxygen saturation (values < 94%) or increases in end-tidal $\text{PCO}_2 > 9 \text{ kPa}$, we will increase the TOF ratio to 0.7 and if this has no effect to 0.8. The experiment is then continued. After the desired TOF ratio is reached, the ventilatory challenges are repeated. The TOF ratio will be measured with the TOF Cuff/TOF watch device at 25 mA. We know from experience that this is an acceptable current.

After the 120-min infusion, the subject is reversed with either placebo (normal saline), or neostigmine 1 mg, or sugammadex 2 mg/kg. We will then repeat the 2-min hypoxic challenges at 5 min interval. When the hypoxic response has returned to control values but not before 60 min have elapsed since reversal we will perform one final hypercapnic ventilatory response.

We expect that all values will normalize within 90 min. The iv line is then removed and after another break of 1 hours (observation period) the subjects is discharged.

The duration of one single experiment is about 4 hours (incl. post experiment observation period). The complete study requires 30 experiment days and will last about 6 months (incl. data analysis)

7. Data and sample size calculation

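### Section 6 takes the iv line out before the 1-hour observation period, so giving the named rescue drug in that hour would first need new venous access (minor; cheap to fix)

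*Combined protocol and SAP*

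**What the plan says.** Section 6 (Study procedures) has an iv line placed on arrival and used for the session. After the 120-min rocuronium infusion and the reversal agent, 2-min hypoxic tests are repeated every 5 min. The final hypercapnic test has a written condition: "When the hypoxic response has returned to control values but not before 60 min have elapsed since reversal". Section 6 then states an expectation, "We expect that all values will normalize within 90 min", and follows it with the closing steps: "The iv line is then removed and after another break of 1 hours (observation period) the subjects is discharged".

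The observation hour belongs to the session. Section 6 counts it in the planned length: "The duration of one single experiment is about 4 hours (incl. post experiment observation period".

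Sugammadex is named as the rescue drug in three places. Section 8 (Monitoring) says: "In case of an emergency sugammadex will be administered to overcome the muscle blockade". Section 4.3 says: "A subject may terminate the study at any moment, and will then receive sugammadex 2 mg/kg to ensure full reversal of the neuromuscular blockade". Section 9 repeats this for a volunteer who demands termination.

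Section 8 also says: "The subject will be closely monitored by measurement of the TOF ratio". The objectives in Section 2 and the sample size text in Section 7.2 both describe recovery from a TOF ratio of 0.6 to 1.0.

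**The concern.** An observation period after a neuromuscular blocking drug is there so that a late problem is noticed and treated. The plan already names the treatment, and the line placed for the session is the quickest route for it. As written, that route is closed just as the observation hour begins. If a volunteer then needed sugammadex, staff would have to cannulate again first.

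What is at stake is a delay in giving a rescue drug to a healthy, awake volunteer. It is a matter of safety procedure and not of inference. It has no bearing on the HVR recovery endpoint, the exponential or regression analyses, or the sample size. It merits a comment because the order of steps is explicitly written, and reversing it costs almost nothing.

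**Working it through.** The plan states no figure for this point, so there is none to reproduce. The check puts the relevant sections in time order and asks two questions: when does the line come out, and is venous access available afterwards?

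**Inputs**
- Infusion ends and reversal is given at t = 120 min (Sections 5 and 5.2).
- The final hypercapnic test comes no earlier than 60 min after reversal, and only once the hypoxic response is back at control (Section 6; Section 5 adds further hypoxic tests if it is not).
- The hypercapnic test consists of two 7-min steps (Section 5.3).
- Observation lasts 1 hour after line removal (Section 6).

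**Earliest line removal, counted from reversal**
- Minimum wait + final test = 60 + 2 × 7 = 74 min.
- This counts only the gas steps. Set-up and changeover time would add to it, hence at least about 74 min.
- If the full 90 min expected for normalization is used, removal falls at 90 min when the final test lies inside that time, or at 90 + 14 = 104 min when it follows.

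**Earliest discharge, counted from reversal**
- 74 + 60 = 134 min.
- The interval from 74 to 134 min, which is the whole observation hour, is spent without the line.

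**Rescue provision against access**

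| Time | iv line | Sugammadex named for use |
|---|---|---|
| Infusion, 0 to 120 min | in place | yes (Sections 4.3, 8, 9) |
| After reversal, up to line removal | in place | yes |
| Observation hour | removed (Section 6) | yes; Section 8 sets no end time and Section 4.3 applies at any time in the study |

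The last row holds the mismatch. No section provides for keeping or replacing the line during the observation hour.

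**What the volunteer's state should be at removal.** The hypoxic response has returned to control, which is the condition for the final test. Section 7.1 says this response also carries the effect on the respiratory muscles, so its return is some evidence of muscle recovery. It is not a full substitute for the TOF ratio, because Section 7.1 sets out to learn whether the two move together. The TOF ratio is itself monitored, and recovery to 1.0 is the range under study. All of this makes a need for rescue after removal unlikely, but it does not explain why the line should come out first.

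**The case against.** The strongest reply is that rescue in the observation hour would hardly ever be needed. Both the emergency use and the early-termination use of sugammadex are aimed at a neuromuscular block, so they matter in that hour only if a block is still present. By then the volunteer has come from a target TOF ratio of only 0.6 and has had at least 60 min of repeated hypoxic tests. He has returned to his control response and has completed a final hypercapnic test. This reply stands as to the size of the risk, and it is why the point is minor. It does not answer the order of steps: an observation hour is planned because something late might happen, and the plan offers no reason to give up access before it.

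Two stronger readings are tempting, and the documents support neither.

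- *Volunteers could be sent home still partly blocked, because no TOF value is written for line removal or discharge.* No such value is written. But Sections 2 and 7.2 describe recovery to a TOF ratio of 1.0 and Section 8 monitors it. Section 6 places removal after a sentence expecting all values to normalize, which can naturally be read to include TOF. An unwritten threshold here is missing detail and does not show that residual block would go unnoticed. The simulated TOF course in Figure 1 is not readable in the text available, so the expected ratio at removal cannot be checked either way.
- *Rescue would be impossible.* The text does not say so. The study takes place in an anesthesiology department's clinical research unit, where placing a new cannula should be feasible. The consequence is a delay of unstated length.

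**Conclusion.** The point holds in a limited form, as a minor and cheap safety improvement. Section 6 places line removal before the observation hour, while the rescue drug named in Sections 4.3, 8 and 9 would need venous access. For each volunteer who completes the session, the gap is the full 60 min of observation, starting at least about 74 min after reversal.

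The conclusion rests on one assumption that the documents do not state: that sugammadex would be given intravenously. It also takes Section 6 at its word on the order of steps. It does not rest on residual block being likely. The documents give no probability of residual block or of an event in that hour, and none is claimed here. No result of the trial depends on this point.

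**What to change.** Reorder the closing steps in Section 6. Suggested wording:

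*After the final hypercapnic response, and once values have normalized, the subject is observed for 1 hour with the iv line in place. The line is removed at the end of this hour, immediately before discharge.*

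The downside is that each volunteer keeps the line for about one hour longer. The observation hour is already planned, so the visit is not lengthened and no test or equipment is added. Endpoints, analyses and sample size stay as they are.
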